This study is designed to compare the efficacy of two treatments for controlling late first stage breakthrough pain during labor: clonidine-bupivacaine versus fentanyl-bupivacaine. Both strategies are used at Columbia University Medical Center (CUMC) in this clinical situation, and there is no clear evidence whether one is superior.

Study Design and Procedures:

After obtaining consent, the patients will be randomized into two groups using a random allocation table. At the onset of late stage breakthrough pain with a Visual Analogue Scale (VAS) greater than or equal to 5/10, subjects will randomly receive either a mixture of 100 mcg

of clonidine and 12.5 mg of bupivacaine for a total volume of 10 ml ("CLON" group) and the other group will receive 100 mcg of fentanyl and 12.5 mg of bupivacaine for a total volume of 10 ml ("FENT" group). Group assignment will be performed by opening a previously prepared numbered opaque envelope containing the assignment "CLO" or "FENT".

The patient will be evaluated every 5 minutes for 15 minutes. If the patient reports a decrease in the VAS pain score by 4 points or more, the treatment will be declared a success. If the patient does not report a decrease in VAS score by 4 or more, the treatment will be declared a failure. If the treatment fails within 25 minutes from the end of injection of the initial study drug, the patient will receive the alternative of the initial treatment, which is 100 mcg of fentanyl or 100 mcg of clonidine (i.e., whichever drug was NOT given in the study mixture) with bupivacaine 12.5mg, diluted to a total of 10ml with sterile saline, via the epidural catheter (the observer will remain blinded to the identity of the medication). If this intervention fails to alleviate the pain, the caretakers will administer 5ml of 2% lidocaine via the epidural catheter. If the pain score still has not fallen by 4 or more points from baseline, 15 min after the dose of lidocaine the epidural catheter will be considered to be non-functioning.

All drug handling/distribution/administration will be conducted in accordance with the policies of the Research Pharmacy and Columbia University Medical Center.

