Demographic and labor data (patient age, height, and weight, parity, hours in labor, cervical dilation and fetal station), details of labor analgesia preceding administration of the study drug (duration, type and amount of epidural or spinal analgesics, or other forms of analgesia), maternal and fetal heart rate and maternal blood pressure prior to and following administration of the study drug will be collected along with other clinical variables.

The study terminates upon delivery of the baby. Maternal and fetal hemodynamic data (maternal BP and pulse, fetal heart rate) and other clinical data will be obtained for 2 hours after the study dose, or until delivery, whichever is earlier. Neonatal Apgar scores as well as the mode of delivery will be collected.

Patients will be recruited by a study investigator after the establishment of labor epidural analgesia. The participants will be patients of the study team physicians. Informed consent with written documentation will be obtained from the research participant.

STATISITCAL PROCEDURES

The primary outcome is "success" or "failure" of the treatment as defined above. A clinically significant difference between the two treatments would be a 0.3 (30%) difference in probabilities for adequate analgesia. Assuming that the inferior treatment is successful in half of all patients, we aim to determine if the superior treatment is successful in 80%. For a power of 80% and an alpha of 0.05, this requires 45 subjects per group, so we plan on studying 100 overall.

To obtain 100 subjects who require a dose for breakthrough pain in the late first stage or second stage of labor, we may need to recruit and consent more than 250 subjects, since women will be

recruited after they are comfortable with their epidural analgesia, and it will not be known if they will eventually need a supplemental dose. Continuous data (VAS, total use of analgesics, maternal and fetal heart rate, maternal blood pressure) will be analyzed using ANOVA (with repeated measurements as appropriate) and categorical data (use of ephedrine, supplemental oxygen, fluid boluses and positional changes associated with administration of analgesics, instrumental delivery, cesarean section) will be analyzed using Chi-Squared analysis with Yates' continuity correction or Fisher's exact test as appropriate.

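### Naming one unconditional exact test in advance, in place of Yates or Fisher as appropriate, would remove an open choice and gain about 1 to 5 points of power within alpha 0.05

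*Combined protocol and SAP*

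**What the plan says.** The Statistical Procedures section defines the primary outcome as success or failure of treatment. The difference of interest is "a 0.3 (30%) difference in probabilities for adequate analgesia", with half of patients succeeding on the worse treatment and 80% on the better. The sample size is given as follows: "For a power of 80% and an alpha of 0.05", "this requires 45 subjects per group, so we plan on studying 100 overall". Sidedness is not stated, but Study Design and Procedures is preceded by the remark that "there is no clear evidence whether one is superior", which implies a two-sided question.

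The same section assigns tests. The sentence beginning "categorical data (use of ephedrine, supplemental oxygen" goes on to list further supportive measures and operative delivery, and prescribes "Chi-Squared analysis with Yates' continuity correction or Fisher's exact test as appropriate". Treatment success is not in that list. These are nevertheless the only tests in the document that could apply to a binary outcome, so the primary test is implied rather than named.

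**The concern.** Two features of that sentence deserve attention.

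First, two tests are offered with no rule for choosing between them. They can fall on opposite sides of 0.05 for the same table, so the primary conclusion could depend on a choice made after the data are seen.

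Second, both tests are conservative for two binomial samples of this size. Their true type I error is below 0.05, and some of the power that the permitted 0.05 would allow goes unused. An unconditional exact test recovers part of it without exceeding 0.05. At stake is a few points of power on the primary comparison, and a result that cannot turn on the choice of test.

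**Working it through.** **Inputs.** From Statistical Procedures: success 0.50 v 0.80, alpha 0.05, power 0.80, 45 per group required, 100 planned overall. Assumed: two-sided testing, and 50 per group as the equal split of 100. Event rates for the secondary items are not given, so those used below are illustrations.

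**The plan's own figure.** With mean rate 0.65, the uncorrected size per group is

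n = [1.960 × √(2 × 0.65 × 0.35) + 0.842 × √(0.50 × 0.50 + 0.80 × 0.20)]² / 0.30² = 38.5, rounded up to 39.

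With the continuity correction,

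n′ = (38.5 / 4) × [1 + √(1 + 4 / (38.5 × 0.30))]² = 44.9, rounded up to 45.

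The stated 45 is reproduced exactly, two-sided and with continuity correction. One-sided it would be 31, or 37 with correction. The trial was therefore sized for a test of the kind it names.

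**Size and power by enumeration.** For each pair of counts (a, b), the probability is the product of two binomial probabilities. Power is the sum over tables with p ≤ 0.05 at rates 0.50 and 0.80. Size is the same sum at a common rate, maximised over that rate. Boschloo's test orders tables by the two-sided Fisher p-value and takes the largest cut-off that keeps maximum size at or below 0.05 (cut-off 0.075 at 45 per group, 0.069 at 50).

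| Split | Test | Maximum size | Power, 50% v 80% |
|---|---|---|---|
| 45 v 45 | Yates | 0.029 | 0.807 |
| 45 v 45 | Fisher | 0.032 | 0.815 |
| 45 v 45 | Boschloo | 0.049 | 0.859 |
| 50 v 50 | Yates or Fisher | 0.035 | 0.853 |
| 50 v 50 | Boschloo | 0.049 | 0.888 |

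The gain is 0.859 − 0.807 = 5.2 points over Yates and 0.859 − 0.815 = 4.4 over Fisher at 45 per group, and 0.888 − 0.853 = 3.5 over either at 50.

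**Unequal arms.** The plan mentions a random allocation table, states no blocking, describes randomization as following consent, and expects about 100 treated women from 250 or more consented. Unequal arms are therefore plausible. With the 50% rate in the smaller arm:

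| Split | Yates power | Fisher power | Boschloo power | Fisher maximum size |
|---|---|---|---|---|
| 44 v 56 | 0.841 | 0.872 | 0.888 | 0.042 |
| 47 v 53 | 0.838 | 0.876 | 0.885 | 0.045 |

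Here Fisher is less conservative, and Boschloo's gain over it falls to 1.6 and 0.9 points. The gain over Yates stays at 4.7 points at both splits.

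**Can the two named tests disagree?** Take 37/47 (79%) v 31/53 (58%). The Yates statistic is 100 × (|37 × 22 − 10 × 31| − 50)² / (47 × 53 × 68 × 32) = 100 × 454² / 5,420,416 = 3.80, below 3.84, so p = 0.051. Fisher gives p = 0.034. At 47 v 53 there are 56 such discordant tables. Equal arms do not always prevent it: at 45 v 45 there are 8, for example 33/45 v 23/45 (Fisher 0.0496, Yates 0.0504). At 50 v 50 the two tests have the same size and power.

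**Rare secondary events, assumed rates.**
- At 50 v 50 and a 5% rate in both arms, the named tests have size 0.007 and Boschloo 0.021.
- At 50 v 50, moving from the named tests to Boschloo raises power from 0.51 to 0.58 for 5% v 20%, and from 0.31 to 0.44 for 2% v 12%.
- At 44 v 56 the last gain disappears: Fisher 0.373, Boschloo 0.374.

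**The case against.** The strongest reply is that nothing planned is lost. The target is 80% power, 45 per group already carries the continuity correction, and both named tests exceed 80% at that size. This stands, and it is why the point is an improvement and not a defect.

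Three stronger readings are tempting, and the documents do not support them.

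- A reader might infer that a true size near 0.03 contradicts the stated alpha of 0.05. Alpha is an upper bound, and a test that stays below it complies. The figure near 0.03 also belongs to equal arms; Fisher's maximum size reaches 0.042 to 0.045 at the unequal splits examined.
- A reader might infer that the named tests hide real differences in ephedrine use or operative delivery. The documents give no rates for these items and set no alpha or power for them. Size below 0.01 needs event rates of about 5% or less and equal arms. At 50 v 50 it is already 0.018 at a 10% rate and 0.028 at 20%, and Fisher's size at a 5% rate is 0.022 at 44 v 56. Boschloo's own size is only 0.002 at a 2% rate with 50 v 50, so low power for rare events comes mainly from having 100 patients.
- A reader might infer that the switch is free in error terms. It is not quite. At 65% success and 50 per group the true type I error rises from 0.030 to 0.046. That is within the limit, but it is a real exchange.

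It is also fair to say that naming Fisher alone would remove the ambiguity. It would, but it would leave the available power unused.

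**Conclusion.** A cheap improvement, not an error. The named tests respect alpha 0.05 and deliver the planned power. What can be bettered is an unruled choice between two tests that can disagree at the 0.05 boundary, and their conservatism. A single pre-named Boschloo test rejects whenever Fisher's does, keeps size at or below 0.05, and adds roughly 1 to 5 points of power for 50% v 80%: least when it replaces Fisher at slightly unequal arms, most when it replaces Yates at 45 per group.

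This rests on two-sided testing, on the planning rates of 50% and 80%, and on the categorical-data sentence being meant to cover the primary outcome. If it is not, no primary test is specified, and the case for naming one is stronger. No benefit should be claimed for the secondary items without event rates.

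**What to change.** Replace the choice of Yates or Fisher with one sentence: the primary success/failure comparison, and the other two-by-two comparisons, will use Boschloo's unconditional exact test at two-sided 0.05, reported with the risk difference and its 95% confidence interval. State that tables are ordered by the two-sided Fisher p-value. Some software instead doubles the smaller one-sided p-value, and the assurance of rejecting whenever the two-sided Fisher test does belongs to the former definition. Keep 45 per group as a conservative planning figure.

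The cost is one sentence in the analysis section and no extra patients; standard software has the test. The drawbacks are that clinical readers know it less well than chi-square, and that the true type I error moves closer to 0.05, though not above it.
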